NOTE: The requirement for maintaining a current disclosure form on file with the University's Conflict of Interest Office extends primarily to Yale University and Yale-New Haven Hospital personnel. **Whether or not they are required to maintain a disclosure form with the University's Conflict of Interest Office, all investigators and individuals deemed otherwise responsible by the PI who are listed on the protocol are required to disclose to the PI any interests that are specific to this protocol.**

SECTION II: GENERAL INFORMATION

1. **Probable Duration of Project:** State the expected duration of the project, including all follow-up and data analysis activities.

The duration of the pilot in its entirety will be 1 year; March 2018-March 2019

2. **Targeted Enrollment:** Give the number of subjects: 40

a. targeted for enrollment at Yale for this protocol 40 If this is a multi-site study, give the total number of subjects targeted across all sites N/A

b expected to sign the consent form 60

c. expected to complete some or all interventions for this protocol? 40

SECTION III: FUNDING, RESEARCH TEAM AND TRAINING

1. **Funding Source:** In IRES
2. **Research Team:** In IRES

SECTION V: RESEARCH PLAN

1. **Statement of Purpose:** State the scientific aim(s) of the study, or the hypotheses to be tested.

HIC# 2000022733

We will conduct a pilot study evaluating the feasibility and acceptability of providing a computer-based program (CBT4CBT), used for the treatment of substance use disorders, in a church setting. Forty Black adults with a current DSM-5 alcohol or substance use disorder will utilize the ‘CBT for CBT’ program over a period of 8 weeks. Primary outcomes will be acceptability and feasibility of providing the treatment in a church setting. If found to be acceptable and feasible, with preliminary promise for reductions in substance use, the next step would be to adapt the computer intervention for this population and conduct a randomized controlled trial.

Specific aims are as follows:

- (1) To determine the feasibility of recruiting Black adults with substance use disorders (BSUD) from within the Black church and immediate surrounding community and retaining BSUD in treatment, within a church setting.
- (2) To evaluate the acceptability of CBT4CBT with BSUD in a church setting and to identify if religious behaviors led by trained church based health advisors (CHA), may increase the likely suitability of this intervention within the Black church.

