- (3) To obtain qualitative data from both CHAs and BSUD about providing substance abuse treatment in a church setting.
- (4) To collect pilot data about the effects of CBT4CBT on substance use, recovery goals and level of functioning among BSUD.

2. **Background:** Describe the background information that led to the plan for this project. Provide references to support the expectation of obtaining useful scientific data.

A. SIGNIFICANCE

A.1. Overview of Research Activities

The overall aim of this proposal is to provide Black adults with substance use disorders (BSUD) access to an evidence-based, web-based, cognitive behavioral therapy intervention (CBT4CBT) and to pilot test it in a church setting. Given low rates of substance abuse treatment initiation and engagement as well as the importance of spirituality and the Black church amongst Black adults, this study will assess the feasibility and acceptability of conducting CBT4CBT in a Black church setting, and measure the effect of CBT4CBT on participant’s substance use, recovery goals and level of functioning.

A.2. BSUD suffer more negative drug-related consequences, but less likely to initiate treatment

Substance Use Disorders (SUD) are one of the most devastating health and social issues confronting this country, causing a tremendous amount of suffering for individuals, families, entire communities, and disproportionately affect minority communities. Black adults use alcohol at lower rates compared with their white counterparts (43.6% vs 57.7%), with nicotine and illicit drug use at the same rate, however Blacks are more likely to suffer negative drug-related consequences, including physical ailments and higher rates of involvement in the criminal justice system. Despite this disparity, Blacks are less likely to initiate substance use treatment when compared with other racial groups, but the reasons accounting for this difference are not well understood. Several theories have been cited for low treatment engagement among Blacks, including societal and cultural stigma associated with accessing substance use treatment,

HIC# 2000022733

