As this is a pilot evaluation of the acceptability and feasibility of providing CBT4CBT in a Black church setting, data analyses will focus on determining whether the results warrant further adaptation of the existing CBT4CBT program. Criteria for this will include (1) measuring acceptability of treatment by giving each participant a post-intervention satisfaction survey as well as a qualitative exit interview, to fully assesses satisfaction with the intervention, perception of outcome, attitudes about spiritual practices accompanying CBT modules, and whether the participant would recommend this program to a friend. (2) Feasibility will be measured by at least 2/3 of participants (N=27) completing the CBT4CBT intervention. Secondary analyses will include significant reductions in drug use, as measured by mean change scores in the severity and quantity of substance use, and functioning over the course of treatment intervention. The proposed sample size (n=40) is adequate to detect this effect.

SECTION VI: RESEARCH INVOLVING DRUGS, BIOLOGICS, PLACEBOS AND DEVICES

N/A

SECTION VII: HUMAN SUBJECTS

1. Subject Population: Provide a detailed description of the types of human subjects who will be recruited into this study.

Participants:

BSUD (20 male and 20 female) who self- identify as Black and want help with drug and/or alcohol problems in the church setting will be recruited from within the church itself, Dixwell Avenue Congregational UCC and the two predominately Black neighborhoods in New Haven, CT, Dixwell and Newhallville, immediately surrounding the church.

CHAs—12 Black church members and leaders who are well versed in the practices of the Black church will be recruited by [name] to serve in this role.

2. Subject classification: Check off all classifications of subjects that will be targeted for enrollment in the research project. Will subjects who may require additional safeguards or other considerations be enrolled in the study? If so, identify the population of subjects requiring special safeguards and provide a justification for their involvement.

- | | | |
|--|--|--|
|  Children |  Healthy |  Fetal material, placenta, or dead fetus |
|  Non-English Speaking |  Prisoners |  Economically disadvantaged persons |

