Data Analysis Plan for a pilot feasibility study of providing substance use treatment in the Black Church

PI: [name] [name]
Data Manager: [name]

Updated 12/3/2020

This study is being conducted to determine the feasibility of recruiting Black adults with substance use disorder from within the Black Church and immediate surrounding community and retaining them in treatment, within a church setting.

A consort diagram will be used to assess the flow of participants from screening through week 8. Since this is a single arm trial cross tabs and ANOVA's will be run to describe the sample on characteristics such as age, sex, education, marital status.

1. We will measure acceptability of treatment by giving each participant a post-intervention satisfaction survey as well as a qualitative exit interview, to fully assesses satisfaction with the intervention, perception of outcome, attitudes about spiritual practices accompanying CBT modules, and whether the participant would recommend this program to a friend.

This will be done by calculating the mean and standard deviation of each question.

2. Feasibility will be measured by at least 2/3 of participants (N=27) completing the CBT4CBT intervention.

This will be a done by calculating the mean and standard deviation of number of sessions attended over the 8-week trial.

3. Secondary analyses will include significant reductions in drug use, as measured by mean change scores in the severity and quantity of substance use, and functioning over the course of treatment intervention.

As the study was implemented this outcome was refined to better reflect the aims of the study (recruiting and retention participants in treatment). A change score will not be calculated.

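### SAP item 3 cancels the only analysis of change in substance use and functioning and puts nothing quantitative in its place, while the aims and the n=40 justification that depend on it still stand

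*SAP*

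**What the plan says.** Protocol Section V.5 (Statistical Considerations) gives the only planned analysis of effect: "Secondary analyses will include significant reductions in drug use, as measured by mean change scores in the severity and quantity of substance use, and functioning". The sentence after it is the whole sample-size justification: "The proposed sample size (n=40) is adequate to detect this effect".

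SAP item 3 repeats the secondary analysis and then explains: "As the study was implemented this outcome was refined to better reflect the aims of the study (recruiting and retention participants in treatment"). It ends: "A change score will not be calculated".

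Three other protocol statements depend on some measure of effect, and neither document amends them:

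- Section V.1, aim 4: "To collect pilot data about the effects of CBT4CBT on substance use, recovery goals and level of functioning among BSUD".
- Section V.2, A.1: the study will assess feasibility and acceptability "and measure the effect of CBT4CBT on" the same three domains.
- Section V.1, Statement of Purpose: "If found to be acceptable and feasible, with preliminary promise for reductions in substance use, the next step" is to adapt the program and run a randomized trial.

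**The concern.** The SAP's reason for the change appeals to the study's aims but names only recruitment and retention, which is Aim 1. Aim 4 is also an aim, and it concerns the outcomes whose analysis was removed. Three things are at stake:

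- Participants provide repeated interviews, urine and breath samples and questionnaires, and no quantitative summary of change from them is planned.
- The Statement of Purpose ties the next step partly to early evidence of reduced use. Under the SAP that evidence would have no measured basis.
- The sample-size sentence now refers to an analysis that will not be run.

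Timing also needs explaining. The SAP is dated 12/3/2020, the protocol planned the project for March 2018 to March 2019, and the SAP says the change came during implementation. Neither document says whether outcome data had been seen. Without a statement on this, a reader cannot rule out selective reporting.

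**Working it through.** **1. What the SAP still analyses.** Its quantitative content is a participant flow diagram, a description of the sample, the mean and SD of each satisfaction question (item 1), and the mean and SD of sessions attended (item 2). None measures substance use, recovery goals or functioning. The closest is "perception of outcome" in item 1, which is the participant's own view.

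**2. What data are scheduled (Table 2).**

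| Domain | Instrument | Time points |
|---|---|---|
| Substance use | Timeline Follow-back | Screening, weekly, post-treatment (none at pre-treatment) |
| Substance use | Urine and breath tests | Screening, pre-treatment, weekly, post-treatment |
| Severity | DSM-5 checklist | Screening, post-treatment |
| Functioning | Quality of Life Scale | Pre- and post-treatment |
| Recovery goals | Recovery Markers Questionnaire | Pre- and post-treatment |

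The Figure 2 legend maps urine and breath tests to substance use and the Recovery Markers Questionnaire to recovery goals. It maps functioning to a Social Functioning Scale that Table 2 does not list. A before-and-after summary is therefore possible in each domain, with the Quality of Life Scale available for functioning.

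**3. Can the protocol's figures be reproduced?** The completion target can: 40 × 2/3 = 26.67, rounded up to 27 (27/40 = 67.5%). The claim that n=40 is adequate cannot be reproduced or refuted, because no effect size, SD, alpha, sidedness or power is stated.

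**4. What precision would a restored estimate have?** Assumptions (not in the documents): mean paired change, independent participants, results in SD units of the change. Evaluable numbers are 40 (everyone), 30 (an illustration) and 27 (the completion target, if only completers had data).

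95% CI half-width = t(0.975, n−1)/√n:

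- n=40: 2.023/6.325 = 0.320
- n=30: 2.045/5.477 = 0.373
- n=27: 2.056/5.196 = 0.396

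**5. What could be detected?** Smallest mean change for a paired t-test at two-sided 0.05 and 80% power (both assumed), from the noncentral t distribution, with the normal approximation (1.960 + 0.842)/√n as a check:

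| n | Noncentral t | Normal check |
|---|---|---|
| 40 | 0.454 | 0.443 |
| 30 | 0.529 | 0.512 |
| 27 | 0.560 | 0.539 |

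Power for a range of true changes, at two-sided 0.05:

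| True change (SD of change) | n=40 | n=27 |
|---|---|---|
| 0.3 | 46% | 32% |
| 0.4 | 69% | 52% |
| 0.5 | 87% | 71% |
| 0.8 | over 99% | 98% |

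Forty could be too few or ample, depending on an effect size the protocol does not state. Participants meet in five cohorts of 8, so positive correlation of outcomes within cohorts would make all of these figures less favourable.

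**The case against.** The strongest reply is that the SAP discloses the change and gives a reason, and that dropping a significance test from a single-arm pilot is sound. A before-and-after change cannot separate the program from other causes. The primary outcomes are acceptability and feasibility, and Section V.5 makes those two the criteria for further adaptation. Aim 4 also speaks of collecting data, which Table 2 still does, and amending the protocol statements would remove the mismatch equally well.

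Much of this stands. The departure is not hidden, the adaptation criteria in Section V.5 are untouched, and no hypothesis test is needed. Two of the gaps also predate the SAP: Section V.5 never planned an analysis of recovery goals, and its sample-size sentence never had inputs. The precision figures describe a restored analysis and do not show that 40 is wrong.

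It does not answer the main point. An argument against testing is not an argument against describing. Collecting data about effects serves little purpose if the data are never summarised. A.1 goes further and promises measurement, and the Statement of Purpose calls for some sign of reduced use. Amending those statements would make the documents consistent but leave the collected data unused.

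**Conclusion.** The concern holds. SAP item 3 removes the only planned analysis of substance use and functioning and replaces it with nothing quantitative. Aim 4, A.1, the condition attached to the next step and the n=40 sentence are not reconciled with that removal. None of Aim 4's three domains has a quantitative summary in the SAP; for recovery goals, Section V.5 had none either.

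This should be fixed, but it does not touch the primary outcomes. The textual finding needs no assumptions. The precision and power figures rest on paired change, independent participants, and assumed alpha, power and evaluable numbers. They show that the adequacy claim is unsupported, not that it is false.

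**What to change.** In SAP item 3, delete the sentence ruling out a change score and add an exploratory analysis of all enrolled participants with available data, whether or not they completed the modules. Report baseline and week-8 summaries, the number missing at week 8, and the mean paired change with 95% CI for:

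- **Substance use (Timeline Follow-back).** Use the screening interview as baseline and state its look-back period. Report days of use, labelled as frequency, plus a quantity measure where available.
- **Severity.** DSM-5 criterion count, screening to post-treatment, with its look-back stated.
- **Functioning.** One measure listed in Table 2, such as the Quality of Life Scale, after reconciling Figure 2 with Table 2.
- **Recovery goals.** The Recovery Markers Questionnaire. This is an addition, since Section V.5 did not plan it.

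Also compare the proportion of negative urine and breath results at pre-treatment and post-treatment, with missing counted as positive as a sensitivity analysis. Label all results as uncontrolled and report them whatever their direction. State when and why the analysis was dropped, and whether outcome data had been seen by then.

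In Section V.5, withdraw the adequacy sentence or replace it with expected precision: assuming independent participants, a 95% CI half-width of about 0.32 SD of the change with 40 evaluable and 0.37 with 30, wider if outcomes are positively correlated within the five cohorts.

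The cost is SAP and protocol wording and a small amount of analysis, with no new data collection. The estimates will be imprecise and uncontrolled, the missing-as-positive result will look pessimistic, and the sample-size statement becomes less favourable. If the sponsor prefers to keep the SAP as it is, Aim 4, A.1, the Statement of Purpose and Section V.5 must be amended to match, and the collected data stay unsummarised.
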